cultured in vitro with no risk of malignant transformation.(Bernardo et al. 2007; Uccelli et al. 2008) So far, there have been no reports in humans of the formation of tumors by in vitro-cultured cells, thus making MSCs amenable for use in transplantation.(see IB and (Lalu et al. 2012)) This is also shown in table 1 of the IB: none of these studies have reported tumorigenesis related to MSC transplantation.

It is also advantageous that MSCs disappear within a short time frame, i.e. do not integrate in the brain, because when they are no longer present, they are not able to lead to tumor formation.

The recent meta-analysis and our own pre-clinical study does not support tumorigenicity of MSC.(Lalu et al. 2012)(Donega et al. 2015) If ectopic tissue formation or a new malignancy is detected in a patient at any time following infusion of the investigational product, the coordinating investigator should be contacted. Information regarding the MSC donor's HLA typing will be provided so that genetic testing for presence of donor-derived MSC can be performed. If MSC donor-derived tissue is present either as malignant tissue or in the malignancy surrounding tissue, this is regarded as a suspect unexpected serious adverse reaction.

f. Pharmacokinetic considerations

Not applicable.

g. Study population

PAIS or cerebral infarction is an important perinatal cause of long-lasting neurodevelopmental problems. The disease manifests itself most often with one-sided convulsions in the first week of life, often accompanied with (asymmetric) hypotonia, lethargy and apnea.(Kirton et al. 2011) When PAIS is suspected clinically this is usually confirmed by MRI. Neuromotor outcome becomes more evident over time and depends largely on the involvement of the corticospinal tracts. Adverse consequences of PAIS include USCP, cognitive dysfunction, epilepsy and speech problems. In 50-75% of infants, PAIS leads to abnormal neuromotor and -developmental outcome or epilepsy.(Fernández-López et al. 2014) Postneonatal epilepsy after PAIS is also often reported, and is associated with larger PAIS.(Wusthoff et al. 2011; van Buuren et al. 2013) The estimated annual mortality rate of neonatal stroke is 3.49/100,000 annually.(Lynch & Nelson 2001) Current treatment options for PAIS mainly focus on controlling convulsions, treatment of hypoglycaemia and associated infections. There is no treatment available that leads to reduction of neonatal brain damage in this severely affected group of infants. This leads to life-long consequences of PAIS and forms a large burden for patients and society. The

overall aim of this project is to meet this need by assessing the safety and feasibility of a cell based treatment strategy for neonates with PAIS.

Patients included in this study will be given MSCs as soon as possible after confirmation of PAIS, but within the first week of onset of presenting symptoms. At time of administration of MSCs, these infants will be admitted to the NICU of our hospital where they can be monitored intensively.

h. Interaction with other products

The potential interactions with other medicinal products, food and other substances have been investigated by the CTF of the UMC Utrecht. No interacting substances were found.

i. Predictability of effect

In this study we will not investigate any therapeutic effects of MSCs. We will only assess safety in terms of (S)AEs.

j. Can effects be managed?

Planned pharmacovigilance actions for potential risks are described below in section 11.2

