PAIS occurs most often in de middle cerebral artery (MCA) with a predilection for the left MCA.(Fernández-López et al. 2014; Benders et al. 2014; Kirton et al. 2011; van der Aa et al. 2014) The most important risk factors are associated with pathological changes that manifest during pregnancy and delivery. Important maternal risk factors include gestational diabetes, pregnancy-induced hypertension and pre-eclampsia, while perinatal factors associated with neonatal stroke are ventouse delivery, emergency Caesarean section, perinatal infections and hypoglycaemia.(Fernández-López et al. 2014; Kirton et al. 2011; Harteman et al. 2012; Martinez-Biarge et al. 2016) Placental pathology has also been linked to PAIS.(Elbers et al. 2011) Coagulation disorders are associated with neonatal stroke, such as genetic polymorphisms of prothrombotic factors (e.g. Factor V Leiden, prothrombin, lipoprotein (a), methylenetetra-hydrofolate reductase or acquired prothrombotic states (e.g. activated protein C). These factors are increasing the risk for PAIS when combined with other risk factors such as perinatal asphyxia, congenital heart diseases or neonatal infections.(Fernández-López et al. 2014)

The disease manifests itself most often with one-sided convulsions in the first week after birth, often accompanied with (asymmetric) hypotonia, lethargy and apnea.(Kirton et al. 2011; van der Aa et al. 2014) When stroke is suspected clinically and on cranial ultrasound, this is usually confirmed by magnetic resonance imaging (MRI). Neuromotor outcome becomes more evident over time and depends largely on the involved cerebral structures. Especially involvement of the internal capsule and the basal ganglia is associated with impaired motor outcome.(figure 1)

[figure not shown]

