2.4 Study Procedures

Recruitment and inclusion

The NICU of the WKZ is known to have most expertise in neonatal stroke. Therefore, infants suspected of having PAIS will be transferred from hospitals in our region of care and also from other hospitals outside our region, to the UMCU and admitted to our NICU, allowing infants to be part of this study. Patients are eligible for our study if they meet our in- and exclusion criteria, PAIS may have been suspected with cranial ultrasound and will be confirmed within 7 days after onset of symptoms by MRI (including 3D-T1, T2 weighted, diffusion weighted imaging [DWI] and DTI sequences) and this PAIS is characterized by a predominantly unilateral ischemic lesion within the territory of the MCA, with involvement of the corticospinal tracts, cortex, white matter and basal ganglia. Following written parental consent, patients will then be included in our study. Parental consent will be obtained as soon as possible after admission at our NICU. Patients with PAIS that are diagnosed more than one week after birth are not eligible for enrolment.

Intervention period

After inclusion in our study, patients will receive MSCs as soon as possible after confirmation of the MCA-stroke, but within the first week of onset of presenting clinical symptoms. Steps to be undertaken before MSC administration include:

- A bacterial culture taken from both nostrils before administration of MSCs.
 Blood samples will be collected before administration of MSCs. Blood samples are taken routinely in the hospital for clinical purposes, but some extra material (0.5-1 mL) will be collected to determine infection markers CRP, procalcitonin and complete blood count. These samples will be combined with routine blood sampling and taken from routinely placed (arterial) catheters.
- 30 minutes prior to delivery of the MSCs, the nose will be cleaned with saline using standard procedures operative at the NICU.

After these procedures have been performed, infants will receive one dose of 50 x 10⁶ MSCs intranasally. We will use a sterile plastic (e.g. 1,0 mL) syringe containing the MSCs to slowly drip the MSCs alternatively in both nostrils.

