From animal models of neonatal stroke we can conclude that no adverse effects have been described for MSC treatment. Our research group has also assessed long-term safety of intranasal MSC treatment. (Donega et al. 2015) At 14 months following HI no significant lesions or neoplasia were observed in the nasal tubinates, brains or other peripheral organs of mice treated intranasally with MSCs. Additionally, it has been shown that MSCs improved sensorimotor and cognitive function for at least 9 and 14 months, respectively. These results provide strong evidence of long-term safety (and efficacy) of MSC treatment following neonatal HI in mice. (Donega et al. 2015) Also a large metaanalysis on MSC treatment for various pathologies does not support tumorigenicity of MSC.(Lalu et al. 2012) Table 1 from the IB summarizes several other studies that performed administration of autologous and allogenic bone marrow derived MSCs in the treatment of several diseases. From these studies with a follow-up time of 2 months to 4 years, it was shown that (adult) patients do not have an increased risk of long-term effects, including tumorigenicity, after allogeneic MSC treatment.

Risk-benefit balance

We can conclude that MSC treatment in newborns with PAIS might be beneficial and no subacute and long-term risks are to be expected based on available evidence. Acute administration reactions, such as subacute temperature increases, are potentially to be expected, but these are expected to be transient, self-limiting and unharmful, based on the available evidence. However, this is the first study in which MSCs will be administered intranasally in humans, so potential risks might be unknown and/or unexpected. Therefore we have planned to perform a pilot (phase I/II) trial to assess safety and feasibility of MSC treatment in newborns with PAIS. Using close monitoring and (preventative) planned actions, as described in chapter 11.1e and 11.2, and tightly regulated stopping rules (see chapter 6.7) we expect to minimize or prevent risks.

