5.5 Description and justification of route of administration and dosage

Administration route

MSCs will be administered intranasally to prevent loss of MSC in peripheral organs and to make sure MSCs will arrive rapidly and efficiently at the injured brain region. From the nasal mucosa, MSCs cross the cribiform plate and migrate throughout the brain using the rostral migratory stream.(Danielyan et al. 2009; Danielyan et al. 2011) In an animal model of neonatal brain injury, it was demonstrated that MSCs were detected in the olfactory bulb, in the subventricular zone of the lateral ventricles and more caudally in the ischemic damaged hippocampus within 2 hours after intranasal administration.(Donega, van

Velthoven, Nijboer, van Bel, et al. 2013). We also showed improved sensorimotor outcome and decrease of gray and white matter loss after intranasal treatment with MSCs compared to vehicle treatment. It was therefore concluded that the nasal route is efficient for MSC transplantation after neonatal brain injury.(van Velthoven et al. 2010b) This finding is confirmed by a study of Wei et al, who treated rats intranasally with bone marrow-derived MSCs. At 24 days following stroke, MSCs were found to significantly reduce infarct size, promote angiogenesis, neurogenesis and neurovascular repair. Rats treated with MSCs had improved sensorimotor and social behavioral outcome compared to their placebo-treated controls.(Wei et al. 2015)

Studies of our group in the newborn baboon have shown that intranasally administered MSCs have the potential to migrate to the injured brain regions of primates(unpublished observations), in accordance with earlier shown studies in mice and rats is known that the olfactory anatomy of primates such as the baboon is more identical to human anatomy than rodent olfactory anatomy. We therefore expect the MSCs to migrate in a similar way in the newborn baby when administered intranasally.

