5.6 Dosages, dosage modifications and method of administration

(Near-)Term infants with PAIS that are included in this study will receive 50 x 10⁶ MSCs in 600µL saline with 20% Human Serum Albumin (HSA) as described in section 5.5. Infants will be put in anti-Trendelenburg (of approximately 10°) position. Thirty minutes prior to delivery of the cells, the nose will be cleaned with saline using standard procedures operative at the NICU. After 30 minutes 0.6 mL MSCs will be slowly dripped into each nostril. This will be done using a sterile plastic (e.g. 1.0 mL) syringe containing the MSCs to slowly drip the MSCs directly in both nostrils.

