6.1.2 Secondary study parameters/endpoints

To determine if MSC treatment in (near-)term infants with PAIS is safe in the subacute setting, patients will be monitored until the age of 3 months. Subacute safety is defined primarily as the absence of treatment-related serious adverse events (SAEs) according to the Consolidated Standards of Reporting Trials (chapter 7.2) until the age of 3 months. Patients will then be asked to report on other SAEs, including infections, during the first three months of age. Whenever their child experiences fever, or other signs of infection/inflammation, there will be tested for bactermia, systemic infections and/or post-administration virus infections.

To determine if MSC treatment in (near-)term infants with PAIS is safe at 3 months in terms of cerebral tumorigenicity, infants will be scanned using MRI prior to MSC treatment and at 3 months of age. Long-term adverse effects on the brain in terms of tumorigenicity will be determined using this MRI, which is part of regular stroke follow-up program. Scans will be assessed by a pediatric radiologist to see if there are any adverse events on the brain (including tumor formation).

All MRI investigations will be performed on a 3.0 Tesla MR system. Infants will be sedated with a combination of chlorpromazine (0.5 mg/kg), pethidine (2 mg/kg), and promethazine (0.5 mg/kg) intramuscularly, which is part of our standard MRI procedure. During MR

examination the neonates will be placed in a vacuum fixation pillow (Med Vac Infant Immobilizer Bag, Radstadt, Austria) to prevent movement. Monitoring will be performed using pulse oximetry (Nonin, Minneapolis, MN) and respiration rate will be observed using the standard Philips equipment (Philips Medical Systems, Best, Netherlands). For hearing protection we will use: Minimuffs® (Natus Medical Incorporated, San Carlos, CA, USA), Earmuffs (EM's 4 Kids, Brisbane, Australia) and a passive acoustic noise dampener, the acoustic hood that properly fitted in the bore of the MRI scanner (Intera, Philips Medical, Best, Holland).

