With respect to possible risks of the present MSC treatment, the most important potential risk factors such as inflammatory actions of MSC therapy with allogeneic human MSCs and an increased risk for malignancies, are intensively investigated in our own preclinical studies and were not found. (Donega et al. 2015) In addition, we found that intranasal administration of human MSCs enhanced secretion of anti-inflammatory cytokines.(Donega, Nijboer, Braccioli, et al. 2014) Additionally, human trials on MSC treatment for adult stroke or other pathologic conditions do not provide evidence for these or other serious adverse events or risks. No single indication has been found in experimental research in the developing animal models that above mentioned complications occur in a higher incidence as compared to non-MSC treated animals, whereas possibility for a substantial better short- and long-term outcome seems very realistic on the basis of previous experimental research data. However, this is the first study administering MSCs intranasally in humans, so potential risks might be unknown and/or unexpected. Therefore, we have planned to perform a pilot (phase I/II) trial to assess safety and feasibility of MSC treatment in newborns with PAIS. Using close monitoring and (preventative) planned actions, as described in chapter 11.1e and 11.2, and tightly regulated stopping rules (see chapter 6.7) we expect to minimize or prevent these risks.

Summary of potential risks

Even though there is no evidence that risks as mentioned below occur in a higher incidence as compared to non-MSC treated animals, these risks will be monitored as part of standard clinical care on the NICU. These risks are based on theoretical mechanisms of action, most likely to occur after systemic administration of MSCs. In general, risks or adverse events related to MSC treatment can be categorized in three groups: acute, subacute and longterm adverse effects.

- 1. Acute adverse effects: Administration Reaction/Toxicity
 - Systolic blood pressure >33% decrease or increase from the baseline during or directly following the intranasal administration of the investigational product

- Diastolic blood pressure >25% decrease or increase from baseline during or directly following the intranasal administration of the investigational product
- Heart rate >33% decrease or increase from baseline during or directly following the infusion of the investigational product

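### In a first intranasal use of MSCs, no dedicated check of the nose after dosing is stated, and the planned analysis cannot show short-lived airway events around dosing

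*Combined protocol and SAP*

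**What the plan says.** **Route and novelty.** Section 11.1e states that "this is the first study administering MSCs intranasally in humans, so potential risks might be unknown and/or unexpected". Section 2.4 gives the method of delivery, by syringe, "to slowly drip the MSCs alternatively in both nostrils". Section 5.5 describes the path: "From the nasal mucosa, MSCs cross the cribiform plate and migrate throughout the brain using the rostral migratory stream".

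**Listed risks.** Sections 5.4 and 11.1e give the same acute list: changes in systolic pressure, diastolic pressure and heart rate; dyspnoea, vomiting, flushing or diarrhoea within 1 hour; fever within 2 hours; exanthema or urticaria within 2 hours. Section 11.1e introduces the listed risks with the sentence "These risks are based on theoretical mechanisms of action, most likely to occur after systemic administration of MSCs".

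**Late harm.** The secondary objective in section 1 is cerebral tumorigenicity. For the MRI, section 6.1.2 says "Scans will be assessed by a pediatric radiologist to see if there are any adverse events on the brain". In support of long-term safety, section 5.4 cites the sponsor's own 14-month study, in which "no significant lesions or neoplasia were observed in the nasal tubinates, brains or other peripheral organs of mice".

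**Capture and analysis.** Section 7.2.1 records all adverse events that are reported or observed, related or not. Section 6.3 monitors vital signs from baseline to at least 24 hours. Section 8.1 compares vital signs and blood values at baseline and at 24 hours by Wilcoxon signed-rank tests, and expresses SAEs as percentages. Sections 6.1.3 and 8.2 list no other parameters.

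**The concern.** The trial is meant to give the first evidence that MSCs given through the nose are safe in newborns with PAIS. The nose receives the dose and is the start of the stated migration path, so bleeding, obstruction, discharge and tissue change at that site are the harms most specific to the route. None is named, and nobody is assigned to look for them after dosing. The animal study relied on for late safety did examine this site; the human plan has no matching examination.

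A second gap concerns timing. Liquid dripped into the nostrils could cause a brief airway event during dosing or soon after, in infants whose disease is "often accompanied with (asymmetric) hypotonia, lethargy and apnea". The planned comparison uses two time points 24 hours apart, and non-serious events have no stated analysis, although the objectives include the occurrence of any adverse event. The trial could therefore report acute safety of the nasal route without a count of the local and airway events that a reader would most want to see.

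**Working it through.** The plan gives no figure for local harm, and N = 10 rests on recruitment feasibility, not on a formula. Its recruitment arithmetic is sound (180,000 / 2300 = 78.3 a year, against about 80 stated) but does not bear on this point. The check is mainly one of content.

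**1. Acute list in 5.4 and 11.1e, item by item**

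| Item | Timed from | Nasal? | Airway? |
|---|---|---|---|
| Systolic pressure | intranasal dose | no | no |
| Diastolic pressure | intranasal dose | no | no |
| Heart rate | infusion | no | no |
| Dyspnoea, vomiting, flushing, diarrhoea | intranasal dose | no | dyspnoea only |
| Fever | intranasal dose | no | no |
| Exanthema, urticaria | intranasal dose | no | no |

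So 0 of 6 items is a nasal event, 1 of 6 contains a respiratory sign, and apnoea and desaturation are absent. Five of the six are timed from the intranasal dose. These counts describe the list; they do not measure risk.

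**2. Other places where the plan could look at the nose**

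- Sections 2.4 and 4.1: nostril culture before dosing; none stated afterwards.
- Section 11.2: monitoring repeats the acute list and adds nausea; no nasal item.
- Section 6.7: no nasal event named. Formation of malignancies is listed without limit of site.
- Sections 11.1e and 11.2: the rule on ectopic tissue or malignancy is not limited to the brain, but it starts only once something is detected.
- Section 6.1.2: MRI read for the brain.

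**3. What the 24-hour comparison can show**

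The signed-rank test uses dᵢ = (value at 24 hours) − (value at baseline) for each infant. If a saturation or breathing measure falls during dosing and recovers before 24 hours, dᵢ is the same as if nothing had happened. The test therefore carries no information on transient events around dosing, whatever the sample size. Section 6.3 also does not say which vital signs are followed.

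**4. What 10 infants could show if the events were sought**

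With 0 events in 10 infants:

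- one-sided 95% upper bound: 1 − 0.05^(1/10) = 25.9%
- upper limit of the two-sided 95% interval: 1 − 0.025^(1/10) = 30.8%

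The chance of at least one case is 1 − (1 − p)^10. The documents give no rate, so p is assumed:

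| Assumed true rate p | Chance of at least one case in 10 |
|---|---|
| 5% | 40% |
| 10% | 65% |
| 20% | 89% |

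These figures apply only if every infant is actually checked.

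**5. Related contradiction in 5.6**

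The product is described as 600 µL in total, yet 0.6 mL is to go into each nostril: 2 × 0.6 = 1.2 mL. Since these statements define the local nasal exposure, they must be reconciled.

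**The case against.** The sponsor can fairly say that the airway is not ignored. Dyspnoea within 1 hour of the intranasal dose is pre-listed and has a planned monitoring action. Vital signs are followed for at least 24 hours, and infants stay on the NICU for at least 4 days. A life-threatening airway event, or one that prolongs the hospital stay, is an SAE and would be reported. All of this stands, so a reader who infers that the nose and airway have no safety read-out at all would go too far.

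Three other strong readings also fail:

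- **That the list is, by the protocol's own account, a list of systemic-route harms.** Section 11.1e says only where these risks are most likely, and most items are timed from the intranasal dose.
- **That an apnoea would go unrecorded if blamed on the stroke.** Section 7.2.1 records events whether or not they are thought related. Attribution matters later, because the primary safety definition counts treatment-related SAEs.
- **That the lower airway receives the whole dose.** The text speaks only of the nostrils.

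The sponsor can add that the turbinates were clear in mice at 14 months, which supports a cerebral endpoint. That lowers the expected risk, but a negative animal result does not replace a look in a first human use.

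Two practical objections also stand. The documents list MRI sequences but not coverage, so the field of view may not include the whole nasal cavity. A pre-dose comparison period could contain the saline cleaning 30 minutes before dosing and perhaps residual MRI sedation (6.1.2), either of which might mask a dosing effect. The fix allows for both.

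**Conclusion.** The point holds in a limited form. No dedicated local nasal assessment after dosing is stated, in the first human use of this route. Airway effects have partial cover, but the planned analysis cannot show transient events around dosing and has no place for non-serious local events.

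The size cannot be put as a rate, because the documents give none. The practical loss is that the trial could not make even the modest statement open to 10 infants, namely an upper bound of 25.9% (one-sided) on a nasal harm not seen. The plan should be changed on this point, but the gap does not invalidate the trial: SAEs, general adverse events and brain imaging are still covered.

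This rests on the protocol text as available. The section 2.5 flowchart is not shown, and the Investigator's Brochure, IMPD, DSMB charter and monitoring plan were not available; a nasal check in one of them cannot be excluded. If one exists, the protocol need only cite it and say how it will be reported.

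**What to change.** 1. **MRI reading (6.1.2 and the matching objective in section 1).** Have the same paediatric radiologist also read the nasal cavity, cribriform plate and olfactory bulbs and tracts on the baseline and 3-month scans, as far as the field of view allows. Record for each scan whether the region is covered. Report the result as cerebral and nasal/olfactory.
2. **Solicited events (5.4, 11.1e, 11.2).** Add nasal bleeding, obstruction and discharge up to discharge from hospital, and apnoea or desaturation during dosing and for 2 hours afterwards. Take both from existing NICU records. The 2-hour window is the one already used for fever and rash.
3. **Analysis (8.1).** Tabulate each solicited event as n/10 with an exact confidence interval, serious or not.
4. **Any pre-dose comparison.** End the comparison period before the saline cleaning, and record the time of MRI sedation.
5. **Section 5.6.** Reconcile the total volume with the volume per nostril.

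The cost is protocol and case-report-form wording plus a few minutes of extra reading for each of 2 × 10 = 20 planned scans. No new procedure or reader is needed. The downside is that some incidental nasal findings will be recorded.
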